The proportion of survivors who are RRT-dependent at 90 days requires special consideration, as the non-inclusion of participants who died might obviate the intergroup balance afforded by randomisation. We will undertake two complementary approaches. First, we will develop a model for the primary outcome to estimate the probabilities of 90-day survival.

We will then use the reciprocals of these probabilities as weights in a logistic regression for RRT dependence, resulting in an inverse probability weighted analysis. The second approach will employ a multinomial regression model to jointly consider the following states: dead at 90 days, alive at 90 days receiving RRT, and alive at 90 days free of RRT. In addition, time-to-event models that incorporate competing risks or multiple outcomes will be considered.

Days alive and free of outcome will be calculated for treatment with RRT through 90 days, vasoactive therapy through 28 days, mechanical ventilation through 28 days, ICU stay through 28 days, and hospital stay from randomisation through 90 days (Table 2). These will be summarised by treatment allocation using means (SDs) or medians (IQRs). Differences will be explored using linear regression and presented as a mean difference (95% CI).

We will obtain a measure of health-related quality of life at 90 days using the EuroQoL EQ-5D-5L scale to enable a cost-effectiveness analysis of the two approaches to RRT initiation ¹² This health economic evaluation will be reported after the publication of the main trial findings.

Analyses of adverse events and serious adverse events

The number and percentage of adverse events and serious adverse events occurring between randomisation and 14 days will be reported for the treatment arm (Table 3).

References

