2.9 Sample size justification

We expect a 90-day mortality of 40% in the standard arm. This mortality rate is compatible with 90-day mortality reported in contemporary cohorts of patients with RRT-requiring AKI in Finland and Australia/New Zealand.^{4,21} There is no clear guidance on the estimated risk reduction afforded by accelerated RRT so we have selected a relative risk reduction of 15% (absolute risk reduction 6%) as recommended by experts to be an effect magnitude that is minimally important and conceivable with this intervention.⁴⁹ With Type I error of 0.05 and power of 0.90, a sample size of 1,359 patients/arm would be required (total 2,718). In order to account for the interim analyses, the required sample size increases to 2,780. After accounting for a combined rate of crossover and dropouts of 3% (as derived from the pilot phase), we will target a total sample size of 2,866.

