the ICU and/or nephrology attending physician and ask if they agree with the statement: "RRT must be initiated immediately in this patient" If the answer is "Yes", the patient will be excluded but may be rescreened for eligibility; and ● the clinicians caring for the patient believe that deferral of RRT is mandated. After fulfilling the above inclusion/ exclusion criteria, the study team will speak to the ICU and/or nephrology attending physician and ask if they agree with the statement: "RRT must be deferred in this patient" If the answer is "Yes", the patient will be excluded but may be rescreened for eligibility.

Randomisation, treatment allocation and blinding

Intervention

Patients enrolled in the STARRT-AKI trial will be randomly allocated to receive either accelerated (early) initiation of RRT, defined as start of RRT within 1 2 hours of fulfilling eligibility, or standard (delayed) initiation of RRT, whereby

RRT initiation is discouraged unless one or more clinical criteria for RRT develop and/or the attending physician determines that deferral of RRT is no longer in the patient's best interest. Eligible patients will be allocated 1 :1 by randomised permuted blocks (of variable size) and stratified by site, using a dedicated web-based platform.

Primary outcome

The primary outcome is all-cause mortality 90 days after randomisation.

[figure not shown]
Secondary outcomes

The secondary outcomes are:

- RRT dependence at 90 days after randomisation among surviving patients;
- composite of death and/or RRT dependence at 90 days after randomisation; ● composite of major adverse kidney events, defined as death, RRT dependence or sustained reduction in kidney function (defined as eGFR < 75% baseline eGFR) at 90 days after randomisation, 1 1 ● eGFR among surviving patients at 90 days after randomisation; ● albuminuria among surviving patients at 90 days after randomisation; ● death in the ICU, at 28 days after randomisation, and inhospital;
- RRT-free days to 90 days after randomisation; ● ventilator-free days and vasoactive therapy-free days to 28 days after randomisation; ● length of ICU stay and ICU-free days to 28 days after randomisation, ● length of hospitalisation and hospitalisation-free days to 90 days after randomisation; and ● health-related quality of life, using the EuroQoL EQ5D-5L scale, among surviving patients at 90 days after randomisation. 1 2

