The STARRT-AKI trial population will include a minimum of 2866 patients, in order to have at least 90% power to detect a 15% relative reduction (6% absolute risk reduction) in the risk of death, assuming an estimated baseline 90-day all-cause mortality of 40%. The baseline mortality rate was based on the available published literature and data from our pilot trial.^{14,15} A 15% relative risk reduction required a total sample of 2718 (1359 patients per arm); however, to account for the three planned interim analyses and an estimated combined rate of crossover, dropout and loss to follow-up of 3%, the total sample size was increased to include a minimum of 2866 patients. Following the planned third interim analysis, performed when 75% of recruitment had been achieved (24 April 2019), the Data Safety Monitoring Board (DSMB) supported the extension of recruitment to achieve a sample size of a minimum of 3000 patients.

Statistical analysis

Analysis principles

Analysis will be performed on an intention-to-treat (ITT) basis. ● All tests will be two-sided and the overall type I error probability for the primary outcome will not exceed 5% ($\alpha = 0.05$) over the three interim analyses by employing an O'Brien—Fleming stopping boundary. This approach gives P values thresholds for stopping at each of the interim analyses of 0.00001473, 0.003045 and 0.0183, respectively, and a required significance level of 0.044 at the final analysis.¹⁶ The primary outcome will be analysed independently by two statisticians. For secondary analyses and endpoints, P values will be reported, but since these are best viewed as exploratory, formal hypothesis testing (ie, for rejection of null hypotheses) will be avoided. ● This SAP and the main STARRT-AKI trial manuscript will only include analyses up to 90 days after randomisation. ● The analysis of one-year outcomes (eg, mortality, dialysis dependence, health-related quality of life) and health economic outcomes will be reported separately and the analytic approach to these outcomes will not be covered in this SAP.

- Pre-specified subgroup analyses will be performed irrespective of the result for the primary outcome.
- Secondary outcome analyses will be performed irrespective of the result for the primary outcome and will be considered exploratory.

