The number and percentage of deaths through 90 days after randomisation will be reported for each treatment group. The primary effect estimate will be the relative risk of 90-day mortality, reported with 95% CI. The absolute risk difference and 95% CI will also be reported. Deaths up to 90 days after randomisation will be compared between the treatment groups using test. Additionally, the odds ratio (OR) (95% CI) will also be determined, primarily to permit comparisons between the primary unadjusted analysis and the various secondary pre-specified adjusted analyses of 90day mortality (Table 2).

Adjusted sensitivity analysis

Death at 90 days will also be analysed, adjusting for baseline characteristics (eg, age, sex, baseline eGFR, Simplified Acute Physiology Score [SAPS] II score at randomisation, surgical status, and presence of sepsis). Continuous variables (eg, age, eGFR and SAPS II score) will be modelled using restricted cubic splines with four knots to accommodate the possibility of non-linear relationships with the log odds of death. The OR and 95% CI will be determined first, primarily to permit comparisons between the unadjusted analysis and the secondary adjusted analyses of 90-day mortality. The adjusted treatment effect will be reported as the adjusted OR (95% CD. Should the adjusted OR be materially different from the unadjusted OR, a second adjusted model will be fit that employs the log link to provide adjusted estimates of the risk ratio. An additional sensitivity analysis will include site as a random effect in a generalised linear mixed model to assess if the variance component is important and affects inference.

Treatment of missing data

If more than 5% of patients from the ITT population are excluded from the adjusted analysis of the primary outcome due to missing data for baseline covariates, missing data will be imputed using fully conditional specification ²⁰ The imputation model will include all covariates required for the adjusted analysis as well as other baseline variables deemed related to the variables for which imputations are required. The multiple imputation will then be performed via chained equations to obtain ten imputed datasets. The adjusted analysis will be performed on the imputed datasets with the results appropriately pooled.

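### The SAP names no comparison model for Day-90 eGFR and no covariates for the free-days regressions; read as unadjusted, the intervals are valid but wider than they need to be

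*SAP*

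**What the plan says.** The SAP's list of secondary outcomes includes "eGFR among surviving patients at 90 days after randomisation". The section on analysis of other secondary outcomes covers RRT dependence, the composites, the free-days outcomes and EQ-5D-5L, but does not say how eGFR is compared. Its row in the Table 2 shell shows a mean and SD per arm.

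For days alive and free of RRT, ventilation, vasoactive therapy, ICU and hospital, the same section says: "Differences will be explored using linear regression and presented as a mean difference (95% CI". It names no covariates. It describes the neighbouring binary outcomes as unadjusted.

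Protocol section 2.10 compares durations of support and stay, and albuminuria, by t-test. For eGFR it gives only a chi-squared test of a 25% decline.

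Covariates do appear for 90-day death. The SAP's adjusted sensitivity analysis is described as "adjusting for baseline characteristics (eg, age, sex, baseline eGFR", and the list goes on to SAPS II, surgical status and sepsis. Age, eGFR and SAPS II enter as four-knot splines. Baseline eGFR and SAPS II are both tabulated in Table 1.

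**The concern.** Baseline eGFR is used to help explain death, but no use of it as a covariate is specified for the same quantity measured 90 days later, where one would expect it to be informative. Both eGFR values come from the CKD-EPI equation, which takes age and sex as inputs (protocol sections 2.2.3 and 2.7.2), so part of the spread between patients is shared by construction. A comparison that ignores this leaves removable variation in the error term, and a real difference in kidney function becomes easier to miss.

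There is also a question of pre-specification. The trial is open-label, and with no eGFR model in the SAP, the method and covariates could be chosen after the results are known.

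Finally, for RRT dependence in survivors the SAP recognises that leaving out the dead can upset the balance from randomisation, and it plans weighting and a multinomial model. Day-90 eGFR has the same restriction to survivors and gets no comparable treatment.

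**Working it through.** **1. The plan's own figure.** Protocol section 2.9 gives the inputs: "We expect a 90-day mortality of 40% in the standard arm" and a "relative risk reduction of 15% (absolute risk reduction 6" percentage points, so p₁ = 0.40, p₂ = 0.34 and the mean is 0.37. With two-sided α = 0.05 and power 0.90:

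n per arm = [1.960·√(2·0.37·0.63) + 1.2816·√(0.40·0.60 + 0.34·0.66)]² / 0.06² = 4.891 / 0.0036 ≈ 1,359.

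This reproduces "With Type I error of 0.05 and power of 0.90, a sample size of 1,359 patients/arm would be required (total 2,718". Taking the interim-adjusted 2,780 as given, 2,780 / 0.97 = 2,866, as stated. The documents give no SD, correlation or precision target for eGFR or free-days, so what follows is in units of the outcome SD.

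**2. Unadjusted precision at N = 2,866 (1,433 per arm).**
- Survivors: at most 1,433 × 0.60 ≈ 860 (standard) and 1,433 × 0.66 ≈ 946 (accelerated), if the planning mortality holds and every survivor has a Day-90 creatinine.
- eGFR 95% half-width: 1.96·√(1/860 + 1/946) = 0.092 SD.
- Free-days 95% half-width, all patients: 1.96·√(2/1,433) = 0.073 SD.

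At the extended minimum of 3,000 these become 0.090 and 0.072 SD. The percentages below do not change.

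**3. Effect of adjustment.** Let R be the multiple correlation of the outcome with the baseline covariates. The half-width is multiplied by √(1 − R²), which is worth 1/(1 − R²) − 1 more patients. R is assumed; I take 0.4 to 0.7 for eGFR and 0.2 to 0.4 for free-days.

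| R | √(1 − R²) | Narrowing | Equivalent extra patients | eGFR half-width (SD) | Free-days half-width (SD) |
|---|---|---|---|---|---|
| 0.2 | 0.980 | 2.0% | 4.2% | – | 0.072 |
| 0.3 | 0.954 | 4.6% | 9.9% | – | 0.070 |
| 0.4 | 0.917 | 8.3% | 19.0% | 0.085 | 0.067 |
| 0.5 | 0.866 | 13.4% | 33.3% | 0.080 | – |
| 0.6 | 0.800 | 20.0% | 56.2% | 0.074 | – |
| 0.7 | 0.714 | 28.6% | 96.1% | 0.066 | – |

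**4. Missing baselines.** Protocol section 2.2.3 expects many patients to lack a pre-hospital creatinine. As a missing-indicator approximation, let a fraction m contribute no gain, so the effective R² is (1 − m)R².
- m = 0.25: narrowing 6.2% (R = 0.4) and 14.6% (R = 0.6).
- m = 0.5: √(1 − 0.5·0.16) = 0.959, narrowing 4.1% (R = 0.4); √(1 − 0.5·0.36) = 0.906, narrowing 9.4% (R = 0.6).

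This credits all of R² to baseline eGFR. Age, sex and SAPS II would keep some of the gain.

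**The case against.** The strongest reply is that the SAP is consistent and the cost is modest. Even the principal analysis of the primary outcome is unadjusted, with adjustment as sensitivity, and adjusted analyses are ruled out for ICU, hospital and 28-day mortality. Secondary outcomes are declared exploratory, and formal testing of them is to be avoided, so no error rate or sample size rests on these intervals. The principal secondary outcome is RRT dependence, not eGFR, and it gets two dedicated analyses. Baseline kidney function also enters through the major adverse kidney events composite, which compares Day-90 eGFR with the patient's own baseline.

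Most of this stands, and it limits the weight of the point. It does not supply the missing eGFR method, and a dichotomy at 75% of baseline does not replace an adjusted comparison of the continuous value. The consistency argument is met by reporting both differences.

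Two stronger readings are tempting. A reader might infer that the SAP prescribes a comparison of raw eGFR means and a free-days regression on treatment alone. It says neither. Both are inferred from silence, supported by the protocol's t-tests, and the SAP's general rule still promises a 95% confidence interval for every treatment effect. A reader might also infer that unadjusted results would be wrong, or that a chance imbalance would pass as an effect. An unadjusted interval already allows for chance imbalance. The systematic problem is the restriction to survivors, and adjustment does not remove that.

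The objection that the SAP's multiple imputation cannot simply be reused also stands: it is triggered by, and specified for, the adjusted analysis of the primary outcome.

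**Conclusion.** The point holds as one of efficiency and under-specification. It is worth acting on for Day-90 eGFR and optional for free-days. No stated figure is wrong, and unadjusted intervals would be valid.

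The size rests on assumed correlations. With complete baselines the eGFR gain is about 8% to 29% in interval width for R of 0.4 to 0.7. The top of that range, equivalent to 96% more survivors, needs R = 0.7 and no missing baselines, and the documents support neither. With half the baselines missing, 4% (R = 0.4) to 9% (R = 0.6) is the more cautious figure. For free-days the assumed gain is 2% to 8%.

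An adjusted eGFR difference would correct measured baseline imbalance among survivors only. It would remain a contrast conditional on survival, and it would not deal with survivors who have no Day-90 creatinine.

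**What to change.** In the SAP's section on other secondary outcomes:

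- **Model.** Analyse Day-90 eGFR by linear regression on treatment with baseline eGFR (spline), age, sex and SAPS II. Report the adjusted mean difference with its 95% confidence interval beside the unadjusted one, and keep arm means and SDs as description.
- **Baseline.** Use the baseline creatinine definition in protocol section 2.2.2: the outpatient value closest to admission within the preceding year, otherwise the lowest in-hospital value.
- **Missing baseline values.** Extend the SAP's imputation explicitly to this analysis for any baseline still missing, with Day-90 eGFR in the imputation model.
- **Interpretation.** State that the adjusted difference is conditional on survival and corrects only measured baseline imbalance among survivors.
- **Free-days.** Optionally add age, SAPS II, sepsis and surgical status. Otherwise say that the regressions contain treatment only.

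The cost is a few sentences and little code, plus a re-specified imputation model. The gain shrinks where baseline eGFR is missing or rests on an in-hospital value that acute illness may already have raised.

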We will perform an analysis of time to death. This analysis will be censored at 90 days after randomisation or on the date the patient was last known to be alive, whichever occurs earlier. A Kaplan—Meier survival curve stratified by randomised group will be used to describe survival rates. Differences in survival will be tested using a log-rank test.

Table 2. Primary and secondary outcomes

	Accelerated Estimate (N = xxxx)	Standard (N = xxxx)	strategy (95% CI)	strategy (95% CI)
Primary outcome, n (%/0)			Relative risk (95% CI)	Mortality
at 90 days xxxx (xx.x%)	xxxx (xx.x%)	XX (xx—xx)	x.xx	
Secondary outcomes, n (%/0)			Relative risk (95% a)	
RRT dependence at 90 days	xx (xx.x%)	XX (xx.x%)	xx (xx—xx)	x.xx
Death or RRT dependence at 90 days	XX (xx.x%)	xx (xx.x%)	XX (xx—xx)	x.xx
MAKE at 90-days	xx (xx.x%)	xx (xx.x%)	xx (xx—xx)	x.xx
ICU mortality	xx (xx.x%)	xx (xx.x%)	xx (xx—xx)	x.xx
28-day mortality	xx (xx.x%)	xx (xx.x%)	xx (xx—xx)	x.xx
Hospital mortality xx (xx.x%)	XX (xx.x%)	xx (xx—xx)	x.xx	Serum creatinine at 90 days (mg/dL) xx (xx.x%) XX (xx.x%) x.xx
eGFR (ml]min/l .73m ² at 90 days), mean (SD)	xxx.x ± x.x	xxx.x ± x.x	x.xx	
Health services use			Mean difference (95% co)	
Received any RRT, n (%/0)	xxxx (xx.x%)	xxxx (xx.x%)	XX (xx—xx)	x.xx
RRT-free days through 90 days, median (IQR)	xx (xx—xx)	XX (xx—xx)	xx (xx—xx)	x.xx
Initial modality CRRT, n (%/0)	xxxx (xx.x%)	xxxx (xx.x%)	XX (xx—xx)	x.xx
CRRT treatment days, median (IQR)	xx (xx—xx)	XX (xx—xx)	xx (xx—xx)	x.xx
Initial modality IHD, n (%/0)	xxxx (xx.x%)	xxxx (xx.x%)	xx (xx—xx)	x.xx
IRRT treatment days, median (IQR)	XX (xx—xx)	xx (xx—xx)	XX (xx—xx)	x.xx
ICU length of stay, median (IQR)				
Survivors	XX (xx—xx)	xx (xx—xx)	XX (xx—xx)	x.xx
Non-survivors	XX (xx—xx)	XX (xx—xx)	x.xx	
Hospital length of stay, median (IQR)				
Survivors	XX (xx—xx)	XX (xx—xx)	xx (xx—xx)	x.xx
Non-survivors	xx (xx—xx)	xx (xx—xx)	XX (xx—xx)	x.xx
Ventilator-free days through 28 days, median (IQR)	XX (xx—xx)	xx (xx—xx)	xx (xx—xx)	x.xx
Vasoactive agent-free days through 28 days, median (IQR)	XX (xx—xx)	xx (xx—xx)	xx (xx—xx)	x.xx
ICU-free days through 28 days, median (IQR)	xx (xx—xx)	XX (xx—xx)	XX (xx—xx)	x.xx
Hospitalisation-free days through 90 days, median	XX (xx—xx)	xx (xx—xx)	xx (xx—xx)	x.xx

(IQR)				
Rehospitalisation through 90 days, n (%/0)	xx (xx.x%)	xx (xx.x%)	XX (xx—xx)	x.xx
Health-related quality of life (EQ-5D-5L), n (%/0)			Mean difference (95% CD)	
EQ-VAS	XX (xx.x%)	xx (xx.x%)	XX (xx—xx)	x.xx

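### Survivor selection is handled for RRT dependence but not for eGFR, EQ-5D-5L or albuminuria, and length of stay is split by survival under a mean-difference heading

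*SAP*

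**What the plan says.** Under Analysis of other secondary outcomes, the SAP singles out RRT dependence among survivors because "the non-inclusion of participants who died might obviate the intergroup balance afforded by randomisation". It plans two responses. The reciprocals of modelled 90-day survival probabilities are used "as weights in a logistic regression for RRT dependence, resulting in an inverse probability weighted analysis". The second response counts death as a state: "multinomial regression model to jointly consider the following states: dead at 90 days, alive at 90 days receiving RRT, and alive at 90 days free" (meaning off RRT). Competing-risk or multiple-outcome time-to-event models are mentioned as a possibility. Protocol section 2.10 carries the same caution, also for RRT dependence only.

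The SAP's list of secondary outcomes restricts three other measures to the same patients:

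- "eGFR among surviving patients at 90 days after randomisation";
- "albuminuria among surviving patients at 90 days after randomisation";
- health-related quality of life on the "EQ5D-5L scale, among surviving patients at 90 days after randomisation".

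None of the three has a survivor adjustment, an estimand or an interpretive warning. Table 2 puts EQ-5D-5L under a mean-difference heading. Albuminuria has no method and no Table 2 row in the SAP; protocol section 2.10 compares it by t-test.

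Table 2 also lists ICU and hospital length of stay in separate rows for survivors and non-survivors, within a block headed by a mean difference. It does not say whether survival is judged at ICU discharge, hospital discharge or day 90.

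**The concern.** Being alive at day 90 is itself an outcome of treatment. If one strategy keeps more patients alive, the two groups of survivors are no longer the randomised groups. That holds for any outcome measured only in survivors, not just RRT dependence, and the SAP gives no reason for treating the same patients differently from one outcome to the next.

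At stake is how a positive trial would be read. If accelerated RRT saves lives and the additional survivors are sicker, the better arm could show lower eGFR, more albuminuria and worse quality of life although no patient was made worse. Length of stay split by survival status conditions on the same post-randomisation event in both strata.

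**Working it through.** **Inputs from the documents.** Standard-arm mortality 40% and an absolute reduction of 6 points, hence 34% (protocol 2.9; SAP, Sample size). Power 90%, two-sided 5% test, 1:1 allocation, total 2,866.

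**Inputs assumed.** The documents give no SD for eGFR and no outcome gap between additional and other survivors. I take SD 25 to 35 and a gap *D* of 10 to 25 mL/min/1.73 m², complete day-90 data, and no patient dying because of accelerated RRT.

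**1. The plan's own figure.** With pooled variance under the null and mean risk 0.37:

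n = [1.960 √(2 × 0.37 × 0.63) + 1.282 √(0.40 × 0.60 + 0.34 × 0.66)]² / 0.06² = 1,359 per arm, or 2,718. This matches. Taking the stated 2,780 after interim inflation, 2,780 / 0.97 = 2,866, which also matches.

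**2. Survivors.** With 1,433 per arm, 1,433 × 0.60 = 860 standard and 1,433 × 0.66 = 946 accelerated patients survive. The additional survivors number 86, a share of 0.06 / 0.66 = 9.1%.

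**3. Bias.** Let patients who would survive in either arm have mean μ and the additional survivors μ − *D*, with no treatment effect on eGFR. The standard-arm survivor mean is μ. The accelerated-arm survivor mean is (60/66)μ + (6/66)(μ − *D*) = μ − 0.091*D*. The unadjusted difference is therefore −0.091*D*.

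**4. Size for eGFR.** Standard error = SD × √(1/860 + 1/946) = 0.0471 × SD: 1.18 at SD 25, 1.41 at SD 30, 1.65 at SD 35.

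| Gap *D* | Bias | Chance of nominal P < 0.05 at SD 30, no true effect |
|---|---|---|
| 10 | −0.9 | 10% |
| 20 | −1.8 | 25% |
| 25 | −2.3 | not computed |

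At the SAP's extended minimum of 3,000 patients the share is unchanged and the standard errors fall only to 1.15 to 1.61.

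**5. Any survivor-only outcome, in SD units.** A gap of 0.25 to 1.0 SD gives a bias of 0.02 to 0.09 SD against a standard error of 0.047 SD. Nominal P < 0.05 then occurs in about 8% to 49% of trials.

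**6. A check on the assumed gap.** A simulation let a shared latent frailty drive survival (loading 0.7) and eGFR (correlation 0.2, 0.4 or 0.6), with mortality 40% versus 34% and no eGFR effect. At SD 30 the bias was −0.4, −0.7 and −1.1. These correspond to gaps of about 4 to 12, at and below the lower end of the assumed range.

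**7. Dependence on the mortality difference.** The share of additional survivors is *d* / (0.60 + *d*): 9.1% at 6 points, 4.8% at 3 points, 1.6% at 1 point and zero at none. At 3 points the eGFR bias for gaps of 10 to 25 is 0.5 to 1.2.

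**The case against.** Much is already in place. The SAP treats all secondary analyses as exploratory and avoids formal hypothesis testing. RRT dependence is the protocol's principal secondary outcome, which is a fair reason to concentrate the extra modelling there. MAKE counts death together with RRT dependence and reduced eGFR. ICU-free and hospitalisation-free days score deaths as zero and are already to be compared by linear regression with a mean difference and interval. EQ-5D-5L is collected mainly for the economic evaluation, which is reported separately. All of this stands and limits the consequence. It does not remove the bias from the survivor-only rows, and albuminuria and EQ-5D-5L have no death-inclusive counterpart in the 90-day analysis.

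The remedy is also open to challenge. Survival weights make survivors stand in for patients who died; they do not identify the patients saved by treatment. They remove the imbalance only as far as measured baseline covariates explain it. That is why weighting belongs as a complementary analysis.

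A reader might infer more than the documents support:

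- *That the SAP plans a plain test of albuminuria.* It gives no method; the t-test is in the protocol.
- *That Table 2 sets out an eGFR treatment effect.* That row is too broken in the available text to show which effect measure is meant.
- *That Table 2 attaches P values to the survival-split stay rows.* No P-value heading is legible. The general statement under Analysis principles that P values accompany secondary endpoints makes it likely, no more.
- *That the comparison of stay relies on those rows.* It does not, given the planned free-days analyses.

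**Conclusion.** The inconsistency is certain; its size is not. The SAP recognises survivor selection for one outcome and leaves it unaddressed for eGFR, EQ-5D-5L and albuminuria in the same patients. Length of stay by survival status, under an effect-estimate heading and with survival undefined in time, has the same weakness.

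Only the 9% share comes from the trial's own figures, and it needs both the full 6-point benefit and no deaths caused by accelerated RRT. The eGFR bias of 0.9 to 2.3 mL/min/1.73 m² rests on an assumed gap. It runs from below one standard error to nearly two (0.9/1.65 to 2.3/1.18), and the frailty simulation points to the lower part of that range or below. That the additional survivors are sicker is plausible but also assumed.

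A reader might infer that the trial would report false harm to kidneys or quality of life. The documents do not support that: under this model the bias vanishes if mortality is equal, and the analyses are labelled exploratory. This is a minor point, worth making because the correction is nearly free. The primary outcome and sample size are untouched.

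**What to change.** In the SAP, under Analysis of other secondary outcomes:

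- Extend the caution about survivors to eGFR, EQ-5D-5L and albuminuria, and carry it into a Table 2 footnote.
- Add a stated complementary analysis of these three outcomes, using the survival weights already planned for RRT dependence, with robust variance.
- State the main comparison for albuminuria, which the SAP currently lacks.

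In Table 2, show ICU and hospital length of stay by survival status descriptively, without effect estimates or P values, and say at what time survival is judged. Take the treatment comparison from the ICU-free and hospitalisation-free days analyses already planned.

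The cost is a few sentences and reuse of a survival model that has to be fitted anyway. The drawback is that weighting corrects only for measured baseline covariates, so the weighted results should be presented with that limit.
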